Neuropsychiatric Interview – Suicidality instrument, (3) actively engaged in individual therapy in the past two months, and/or receiving couple's or group therapy in the past two months if that therapy focuses on PTSD at a frequency of once per month or more, (4) scheduled to receive a future individual therapy appointment, or a future couples' or group therapy appointment if that therapy focuses on PTSD, at a frequency of once per month or more, (5) moderate or severe alcohol use disorder or any non-alcohol substance use disorder in the past year excluding mild cannabis or any nicotine abuse, (6) acute psychosis, psychotic episode, or psychotic disorder diagnosis within the past year, (7) homicidality, and (8) unstable administration schedule or dosing of any antidepressant, anxiolytic, or sedative-hypnotic (i.e., will exclude for any related medication changes in the four weeks prior to the eligibility interview). Furthermore, women who participated in earlier phases of the research (qualitative interviews and the pilot study) were not included. These criteria are consistent with PTSD RCTs and PTSD telehealth research (Morland et al., 2009; Schnurr et al., 2003).

**Study procedure.** The study involved three assessment phases: eligibility, baseline, and follow-up (post-treatment and 3- and 6-month follow-ups). The eligibility interview was conducted by a study assessor via telephone. Baseline and follow-up assessments were conducted online. Participants were randomized to condition following the baseline assessment.

***Eligibility screener and interview.*** When interested women Veterans contacted the study office, study staff conducted a pre-consent eligibility screening, which consisted of questions corresponding to inclusion/exclusion criteria. The purpose of the pre-consent eligibility screening was to quickly determine which candidates are most likely to qualify, thus eliminating the need to conduct consent and full eligibility interviews for all potential participants. If patients were found to be eligible following the pre-consent eligibility screening, study staff reviewed the

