consent, answered any questions, and mailed the consent form to the participant to obtain written consent. The full eligibility interview was scheduled at this time and conducted only when written, signed consent had been received in the study office. The full eligibility interview included a collection of demographic information as well as the Mini International Neuropsychiatric Interview (MINI) to assess substance use disorders (Lecubrier et al., 1997) and the CAPS-5 (Weathers et al., 2013). PTSD diagnosis on the gold-standard CAPS was required for study eligibility. The staff member who conducted the eligibility interview in the role of study assessor did not serve as the participant's study coach to avoid potential bias during the assessment. If the interval between the eligibility interview and baseline assessments was longer than four weeks, we required re-administration of CAPS via telephone to ensure PTSD status.

***Baseline and follow-up assessments.*** The baseline and follow-up assessments (at post-treatment and 3- and 6-month follow-ups) consisted of an online survey hosted by SurveyMonkey (SurveyMonkey Inc., Palo Alto, CA). Information collected during the online baseline assessment served as a baseline from which to evaluate the efficacy of the study intervention on the primary outcome (PTSD symptom severity) and secondary outcomes (depression and quality of life). Information about concurrent treatment that might moderate the efficacy of the study intervention ("co-therapies") was also gathered at the baseline assessment (e.g., mental health specialty visits, PTSD-related pharmacotherapy use, and chaplain or similar community support resources) and throughout the course of the study. Following the baseline assessment, patients were randomly assigned to one of the study conditions. Participants received \$25 for the baseline assessment, \$30 for each of the three follow-up assessments, and a \$35 bonus for completing all assessments (for a total maximum of \$150).

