To account for repeated measures within subjects, we used a linear mixed effects model for the analysis of the primary outcome, PCL-5, with the subject treated as a random effect. We have PCL-5 measures at four times during the course of the study: at baseline, 8 weeks (the first post-treatment assessment), and 3 and 6 months post-treatment. The response (dependent) variable was PCL-5 score, and the predictor (explanatory) variables included treatment group, assessment visit (treated as categorical), and a treatment group by assessment visit interaction term, along with the covariates trauma category and rural status. A significant treatment group by visit interaction term indicates a significant difference in change from baseline between treatment groups. Results include adjusted means, standard errors, and 95% confidence intervals for each group at each time, confidence intervals for change from baseline at each time within each group, confidence intervals for differences in change from baseline between the two groups at each time, p-values, and effect sizes. We also used linear mixed effects models for the two secondary outcomes, depression and quality of life.

Linear mixed effects models easily accommodate missing values. We compared the rate and timing of dropouts between treatment groups, and also baseline demographics and outcome scores between treatment completers and non-completers. If necessary, we will perform sensitivity analyses by using only participants who were treatment completers and using multiple imputation to deal with missing values.

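### The primary PCL-5 model gives each arm its own baseline mean and leaves the covariance unstated; a common-baseline model with an unstructured covariance would use precision now left unused, though printed intervals need not be narrower

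*Combined protocol and SAP*

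**What the plan says.** RCT data analytic strategy specifies a "linear mixed effects model for the analysis of the primary outcome, PCL-5, with the subject treated as a random effect". The responses are PCL-5 at baseline, 8 weeks, and 3 and 6 months post-treatment. In the mean model, "the predictor (explanatory) variables included treatment group, assessment visit (treated as categorical), and a treatment group by assessment visit interaction term"; trauma category and rural status are the only covariates. The treatment effect is read from the interaction: "A significant treatment group by visit interaction term indicates a significant difference in change from baseline between treatment groups". The section also promises "confidence intervals for differences in change from baseline between the two groups at each time". No residual covariance is stated. On incomplete data it says "Linear mixed effects models easily accommodate missing values", and allows completer-only and multiple-imputation sensitivity analyses if needed.

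Study procedure says "Participants were randomized to condition following the baseline assessment", and Baseline and follow-up assessments repeats it: "Following the baseline assessment, patients were randomly assigned to one of the study conditions". On entry, "PTSD diagnosis on the gold-standard CAPS was required for study eligibility".

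Power describes a pilot whose size is set by budget and timeline and which is meant, among other things, to give first estimates of effect size. It states 80% power for an effect of 0.68 with 35 per group.

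**The concern.** A free group main effect with baseline among the responses lets the two arms have different baseline means. Because allocation came after the baseline survey, any baseline difference is chance. The planned contrast subtracts that difference in full, where the best linear adjustment subtracts only the part that carries forward to follow-up.

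The covariance is a second matter. A subject random effect with nothing further would usually be read as a random intercept, although the plan does not say so. That structure gives all visits one variance and all pairs of visits one correlation. If follow-up visits correlate sufficiently more with each other than with baseline, the standard error of change from baseline is too small.

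With N fixed by budget, precision and honest intervals are what the analysis can still improve.

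**Working it through.** **Inputs.** From the plan: 35 per arm, two-sided 5%, effect 0.68 (Power); SD of change 8, 15, 22 (Table 1); at most 30% dropout (Power); test-retest r = .84 (Primary outcome). Assumed, because the documents do not give them: ρ, the baseline-to-follow-up correlation (0.3, 0.5, 0.7, 0.84, the last borrowed from the test-retest figure); k, follow-up SD divided by baseline SD (1, 1.2, 1.4); f, the correlation between follow-up visits. Entry on a CAPS-5 diagnosis makes k above 1 plausible.

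**The plan's own figures.** A two-sample t test with 68 df has 80.1% power at 0.68. Half-widths t(0.975, 68) × SD × √(2/35) are 3.82, 7.16 and 10.49, matching Table 1. Both are correct for a change-score comparison at one visit.

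**Common baseline, complete data.** In units of baseline variance:
- variance of raw change: 1 + k² − 2ρk
- variance after baseline adjustment: k²(1 − ρ²)
- difference: (1 − ρk)², never negative and zero when ρk = 1

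Example, k = 1 and ρ = 0.5: 1.00 against 0.75, a 25% cut. Example, k = 1.2 and ρ = 0.5: 1.24 against 1.08, a 13% cut.

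The half-width multiplier below is relative to the change-score interval. It comes from simulation (20,000 trials per setting) and includes the 1–2% variance cost of estimating the slope. The detectable effect is 0.68 × √(variance ratio), in SD-of-change units, for one visit and without that cost.

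| k | Quantity | ρ 0.3 | 0.5 | 0.7 | 0.84 |
|---|---|---|---|---|---|
| 1 | variance cut | 35% | 25% | 15% | 8% |
| 1 | half-width multiplier | 0.81 | 0.87 | 0.93 | 0.97 |
| 1 | detectable effect | 0.55 | 0.59 | 0.63 | 0.65 |
| 1.2 | variance cut | 24% | 13% | 3% | 0% |
| 1.2 | half-width multiplier | 0.88 | 0.94 | 0.99 | 1.01 |
| 1.2 | detectable effect | 0.59 | 0.63 | 0.67 | 0.68 |
| 1.4 | variance cut | 16% | 6% | 0% | 5% |
| 1.4 | half-width multiplier | 0.92 | 0.98 | 1.01 | 0.98 |
| 1.4 | detectable effect | 0.62 | 0.66 | 0.68 | 0.66 |

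At SD 15 the half-width of 7.2 becomes 5.8 to 7.2.

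**Random-intercept reading, complete data.** The model's SE pools the variance of differences over all six pairs of visits, three with baseline and three between follow-ups. Hence (model SE / true SE)² = ½ + k²(1 − f)/(1 + k² − 2ρk). At k = 1, ρ = 0.7, f = 0.8 this is ½ + 0.2/0.6 = 0.833, a ratio of 0.91. With f = ρ + 0.1:

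| k | Quantity | ρ 0.3 | 0.5 | 0.7 | 0.84 |
|---|---|---|---|---|---|
| 1 | model SE / true SE | 0.96 | 0.95 | 0.91 | 0.83 |
| 1 | coverage of 95% interval | 94.1% | 93.5% | 92.7% | 89.4% |
| 1 | new width / planned width | 0.85 | 0.93 | 1.03 | 1.18 |
| 1.2 | coverage of 95% interval | 95.1% | 94.7% | 93.6% | 90.2% |
| 1.2 | new width / planned width | 0.89 | 0.97 | 1.07 | 1.21 |
| 1.4 | coverage of 95% interval | 95.7% | 95.1% | 93.4% | 89.5% |
| 1.4 | new width / planned width | 0.91 | 0.99 | 1.08 | 1.19 |

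The replacement covers 94.7–95.4% in these settings. If all correlations are equal and k = 1, the random-intercept SE is exactly right and the width ratios are 0.82/0.88/0.94/0.98.

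**With 30% dropout.** Assumed per arm: 10 baseline only, 2.5 lost after 8 weeks, 2.5 lost after 3 months, 35 complete. Replacing a random-intercept, free-baseline model then cuts the true variance by about 28/20/12/6% at k = 1, 18/10/3/2% at k = 1.2 and 12/5/2/8% at k = 1.4.

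Bias was checked with a true 6-month difference of −7, change SD 15 and dropout depending on the last observed score. The random-intercept model gives −6.9 to −7.05 at k = 1, and −7.0 when both arms share one dropout rule. If higher scorers leave more often in one arm only, the error is 0.3 to 0.5 points at k = 1.2 and 0.8 at k = 1.4. With opposite rules it is 0.5 to 0.9 and 1.7. The sign depends on which arm loses the higher scorers. The replacement stays at −6.9 to −7.1. Trauma category and rural status were not simulated.

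**The case against.** The planned model is a standard longitudinal specification. It matches the stated target, difference in change from baseline, and agrees with Table 1. Nothing in it is biased under randomisation with complete data, so this is a preference about efficiency in a pilot. That stands, and it is why the point is graded only as something to consider.

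The gain may be close to nil. Where ρk is near 1 there is nothing to recover, and CAPS-5 entry makes k above 1 plausible. This stands and is why the range is shown. The detectable effects are also for a single visit; power for the three-degree-of-freedom joint test was not computed.

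The random intercept is a reading of the text, and the worst coverage (89–90%) needs follow-up correlations of 0.94, above the only reliability figure the plan prints. At ρ of 0.5 or below coverage is 93.5–95.7%. What the text itself supports is that the covariance must be stated. Part of the dropout gain at k = 1.4 is also due to the covariance: against a free-baseline unstructured model it is about 12/4/0/4%. The larger biases need arm-specific, score-dependent dropout together with k above 1, and the plan does compare dropout between arms and allow multiple imputation.

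These points limit the size of the gain. They do not remove the case for a change that needs no further data.

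**Conclusion.** The point holds as an efficiency improvement with a gap in specification, not as an error. With the covariance held unstructured, a common baseline mean narrows the interval or leaves it within about 1%: multipliers run from 0.81 to 1.01 over the assumed ρ and k. Replacing a random-intercept covariance is a separate step. It can widen the printed interval, by up to about 20% in the most extreme settings above, because it corrects an SE that was too small.

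The change does not make the trial confirmatory. Even the lowest detectable effect, 0.55, exceeds every effect cited under Power (0.41, 0.10, 0.23, 0.47, 0.08) except 0.95. The sizes rest on correlations and SD ratios that the documents do not give, and with dropout they also rest on data missing at random.

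**What to change.** In RCT data analytic strategy, state the covariance structure. Fit one common baseline mean, visit, and group-by-follow-up-visit terms, keeping trauma category and rural status, with an unstructured visit covariance and Kenward-Roger degrees of freedom. Replace the interaction test by the joint test of the three group-by-follow-up-visit terms, and report the interval at each visit from the same model. Do the same for PHQ-8 and Q-LES-Q-SF.

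Give the order of fallbacks in advance. The form with baseline as a covariate should serve only for non-convergence, since it drops women with a baseline score alone, whom the intent-to-treat definition includes.

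No new data are needed; the text changes in the mean model and in the covariance. The cost is 10 covariance parameters instead of the 2 of a random intercept, a 1–2% variance penalty for the slope, and intervals that may print similar or somewhat wider. The analysis text is largely in the past tense, so if outcomes have already been seen the planned model should stay primary, with this as a labelled supplementary analysis.

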**Randomization.** We used the Sealed Envelope™ program (Sealed Envelope Ltd., 2016) to generate a randomization table to condition (1:1 allocation ratio) using a permuted block design with block sizes of two and four to maximize the likelihood of a balanced sample size across arms (Schulz & Grimes, 2002), and stratifying by rural status to facilitate exploratory analyses of the impact of this variable on trial outcomes and to maximize the likelihood of balance across arms on this potential characteristic (Kernan et al., 1999). We defined rural status as living more than 40 miles away from the closest VA medical facility, in line with eligibility criteria used by the Veterans Access, Choice, and Accountability Act and shown to be a marker indicating decreased likelihood of receiving psychotherapy (Pfeiffer et al., 2010).

**DESTRESS-WV intervention.** For the DESTRESS-WV condition, the initial telephone session with the study coach served to 1) provide brief psychoeducation regarding PTSD; 2) complete a safety plan that is individualized to the patient for times when she is distressed; 3) introduce the intervention model, the study coach role, and the participant's role; 4) introduce the patient to the website's structure; and 5) problem-solve any obstacles to using the website. Participants were asked to log on the website twice a week each week for eight weeks and complete different homework activities. Nonetheless, up to 12 weeks of access was provided. The coach called the participants once a week at an agreed upon time while they were completing the program to monitor symptoms and safety, review progress through the website, provide encouragement, review a particular skill or strategy when applicable, review barriers to treatment compliance, and address barriers to treatment (target call time is 15 minutes). The coach had access to a back-end of the DESTRESS-WV website where she monitored participants' progress, and this was monitored weekly between every study coach call.

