All participants who withdrew from the treatment protocol were given the option of continuing to provide information at the follow-up assessments for intent-to-treat analyses of outcomes. Additionally, participants randomized to DESTRESS-WV were reminded of the study office phone number and the Veterans Crisis Line during each logon. Participants were also reminded of these phone numbers and other resources after each follow-up assessment.

**Power.** This is a pilot RCT designed to provide estimates of feasibility of the treatment approach, dropout rates, acceptability, and initial effect sizes. The study's budget and timeline allows us to plan to randomize 100 participants. For the primary outcome, Litz et al. (2007) observed a differential effect size of 0.41 at 8 weeks ( $n = 33$ ), 0.10 at 3 months ( $n = 24$ ), and 0.95 at 6 months ( $n = 18$ ) when comparing change from baseline in PTSD symptoms for participants randomized to DESTRESS ( $n = 24$ ) versus supportive counseling ( $n = 21$ ), with an overall dropout rate of 27% prior to the end of 8 weeks of therapy. In a second trial of DESTRESS by Engel et al. (2015) where participants were randomized to optimized usual care ( $n = 37$ ) or DESTRESS ( $n = 43$ ), the 6-week effect size was 0.23 ( $n = 64$ ), the 12-week effect size was 0.47 ( $n = 62$ ), and the 18-week effect size was 0.08 ( $n = 66$ ), with an overall dropout rate of 18%.

As noted above, we hypothesized no more than 30% of participants will dropout prior to the end of the study. Thus, with the goal of randomizing 100 participants and assuming a sample size of at least  $n = 35$  participants per group, we have 80% power to detect an effect size of 0.68 using a two-sided Type I error rate of 5%.

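### Rural status and trauma category are listed only as main effects in the primary mixed model, so they adjust the reported group means but essentially not the difference in change from baseline, which is the treatment effect.

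*Combined protocol and SAP*

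**What the plan says.** The Randomization section of the combined protocol and SAP allocates 1:1 in permuted blocks of two and four, "stratifying by rural status to facilitate exploratory analyses of the impact of this variable on trial outcomes" and to help balance the arms on that factor. Rural status has two levels, set by a 40-mile distance from the nearest VA facility. Trauma category is not a stratification factor.

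The RCT data analytic strategy section fits a linear mixed model with subject as a random effect. The response is the PCL-5 score at four times, of which baseline is one. The predictors are treatment group, visit as a category and their interaction, "along with the covariates trauma category and rural status". No other interaction is listed. The treatment effect is read as follows: "A significant treatment group by visit interaction term indicates a significant difference in change from baseline between treatment groups". The outputs include adjusted means by group and time and, as a separate item, confidence intervals for the between-group differences in change. Mixed models are also planned for depression and quality of life.

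The Power section expects substantial attrition: "we hypothesized no more than 30% of participants will dropout prior to the end of the study".

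**The concern.** A reader who sees the stratification factor among the covariates will assume that the treatment comparison is adjusted for it. In this model it is not. A woman's rural status and trauma category do not change over time, and without a visit interaction each shifts all four of her expected scores equally. The treatment effect is a difference of changes, so the shift subtracts out.

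Three things are at stake. First, the estimate does not use whatever precision the stratification factor and trauma category could give about change. Second, its standard error does not reflect the stratified design. Third, if rural women both drop out at different rates by arm and change by different amounts, the model has no term to carry that difference.

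**Working it through.** **1. The plan's own figures.** The Power section states that "we have 80% power to detect an effect size of 0.68" with 35 per group at a two-sided 5% level. Evaluable n is 100 × 0.70 / 2 = 35 per arm. A noncentral-t two-sample calculation gives power 0.801 at d = 0.68 and a detectable d of 0.679 at 80% power. The normal approximation gives power 0.812. Table 1 half-widths, t(0.975; 68) × SD × √(2/35), come to 3.8, 7.2 and 10.5 for SD 8, 15 and 22, as printed. All reproduce, and none depends on the covariates.

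**2. Algebra of the listed model.** Let G be arm, R rural status, T trauma category (one indicator shown for brevity) and t the visit, with t = 0 at baseline:

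E[Y(t)] = b0 + b1·G + v(t) + d(t)·G + c1·R + c2·T

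Change from baseline: E[Y(t)] − E[Y(0)] = [v(t) − v(0)] + [d(t) − d(0)]·G

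Difference in change between arms: d(t) − d(0)

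Neither c1 nor c2 remains. They affect only the level of the means and the group difference at baseline. Adding R by visit and T by visit would put terms r(t)·R and s(t)·T into the change equation, and the arm contrast would then be conditional on them.

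**3. Numerical check.** The documents give no covariate effects, variance components or rural share, so these are assumptions:
- 100 women, 50 per arm, 30% rural in each arm, and three trauma categories assigned at random.
- Subject SD 10 and residual SD 10, so the SD of change is √(2 × 10²) = 14.1, close to the middle row of Table 1.
- A 7-point treatment effect.
- Covariate effects on change either zero, or 8 points for rural status and 4 points per trauma-category step.
- Dropout either none or about 30%, and higher in rural women (45% against 24%; 0.3 × 45 + 0.7 × 24 = 30.3%).

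Each scenario used 60 simulated trials and a random-intercept REML fit.

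Effect of adding the two main effects, as the plan does:

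| Dropout | Covariate effect on change | Mean shift in interaction estimate | Largest shift | Largest SE difference |
|---|---|---|---|---|
| None | None | under 10⁻¹² | under 10⁻¹² | under 0.00003 |
| None | Yes | under 10⁻¹² | under 10⁻¹² | under 0.00003 |
| About 30% | None | 0.11 | 0.48 | 0.03 |
| About 30% | Yes | 0.20 | 0.69 | 0.04 |

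The standard errors are about 3, so the mean shift under dropout is at most 0.20 / 3 ≈ 0.07 of a standard error. It arises only from between-woman information in incomplete records. A further refit, with about 30% or more dropout, gave shifts of up to about 0.6 to 2 points in single trials. The influence can therefore be larger in one data set, but it is incidental and is not the intended adjustment.

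Effect of adding the by-visit terms, against the model without covariates:

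| Dropout | Covariate effect on change | Mean shift | Largest shift | Mean SE, without → with |
|---|---|---|---|---|
| None | None | 0.33 | 2.3 | 2.81 → 2.84 (+1.2%) |
| None | Yes | 0.56 | 3.0 | 2.89 → 2.84 (−1.7%) |
| About 30% | None | 0.39 | 2.0 | at 6 months 3.21 → 3.25 (+1.3%) |
| About 30% | Yes | 0.83 | 3.3 | at 6 months 3.33 → 3.25 (−2.3%) |

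The 0.33 arises where the covariates do nothing to change, so part of every shift in this table is noise and not bias removed.

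**4. Dropout that depends on arm and rural status.** In the simulations above, dropout did not depend on arm. In a separate simulation it depended on arm and rural status, and rural status affected change. The main-effects model then left a bias, which the by-visit terms removed. Its size depends on inputs that the documents do not give, so no figure is offered.

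**The case against.** Several stronger readings are tempting, and the documents do not support them.

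*Chance imbalance in trauma category passes fully into the treatment effect.* It does not. Differencing already removes any constant effect on PCL-5 level. Only an effect on change is left, and the documents give no evidence of one. For illustration, an assumed 20-percentage-point imbalance with an assumed 7-point difference in change shifts the estimate by 0.20 × 7 = 1.4 points. At SD 15 and 35 per arm the standard error is 15 × √(2/35) = 3.6, so this is about 0.4 of a standard error. It is random error that the interval already covers, not bias.

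*The plan claims that its treatment contrasts are adjusted.* It calls the means adjusted, and they are. It lists the differences in change separately, without that word.

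*The promised rural analysis is impossible.* The Randomization section mentions exploratory analyses but does not place them in the primary model or say that they concern moderation. The listed model does estimate an association of rural status with PCL-5 level. That no exploratory rural model is written out is only missing detail.

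*The primary analysis is invalid.* Stratified 1:1 blocks should keep rural status roughly balanced, and omitting by-visit terms mainly costs a little efficiency. This is also a pilot intended to give initial effect sizes.

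Two further points stand. The predictor list does not expressly exclude a by-visit term, so if one was fitted the text need only say so. And most of the section is in the past tense, so replacing the primary model may mean changing it after the data are known. Neither restores adjustment to the contrast as the plan describes it.

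**Conclusion.** The point holds in a limited form. In the model as listed, the coefficients of rural status and trauma category cancel exactly from the difference in change from baseline. The estimates are identical with and without them when data are complete, and with about 30% dropout the influence is small on average and indirect. The treatment contrast therefore does not account for any effect of the stratification factor on change.

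The cancellation rests on algebra and on reading the predictor list as complete. The size rests on assumed covariate effects, variances and dropout patterns: standard errors about 1 to 4% different in either direction, and possible bias only if dropout depends on both arm and rural status and rural status affects change. It is a modest mismatch between apparent and actual adjustment that is cheap to correct. It does not undermine the trial's validity.

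**What to change.** In the RCT data analytic strategy section, add rural status by visit to the mixed models for PCL-5, depression and quality of life. Add trauma category by visit where category sizes allow. Read the group-by-visit contrasts from those models, and state which outputs are covariate-adjusted. If by-visit terms were already fitted, say so.

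If results are already known, keep the planned model as primary, report the by-visit model as a labelled supplementary analysis, and describe the planned contrasts as effectively unadjusted for the two covariates. If a rural analysis is intended, a sentence specifying it as a separate exploratory model would supply the missing detail.

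The cost is (2 − 1) × 3 = 3 extra parameters for rural status by visit, and (3 − 1) × 3 = 6 more if trauma has three categories, a number that the documents do not give. Standard errors would be about 1 to 4% wider if neither covariate predicts change. Sparse trauma categories would cost more, hence the condition on category size. No sample-size or power figure changes.
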